17.2.2 Criteria for Dose Escalation

The following criteria must be met to proceed to the next dose level:

- No new ECG findings suggestive of cardiac disease
- No confirmed and clinically significant elevated cardiac troponin I levels
- No case of a disease that might be immune mediated and is judged to be possibly, probably or definitely related to IMP, such as acute arthritis, severe generalized rash, or glomerulonephritis
- No pattern of reactogenicity or adverse events suggestive of autoimmune disease or immune mediated disease
- No serious adverse event which is assessed as probably or definitely related to the IMP
- No volunteer death which is assessed as possibly, probably or definitely related to the IMP

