5.0 STUDY DESIGN

The study is a Phase 1 randomized, placebo-controlled, double-blind, dose-escalation clinical trial in healthy male adult volunteers to evaluate the safety and expression of a single intramuscular administration of rAAV1-PG9DP at $4x10^{12}vg$, $4x10^{13}vg$, $8x10^{13}vg$ and $1.2x10^{14}vg$.

Sentinel recipients

The rAAV1-PG9DP administrations escalate by dosage as shown below in Table 1, Study Design. In Groups A-D, the first 3 volunteer injections will be separated by 7 days, to allow for observation of IMP-related adverse events in the first two participants. Because there is one placebo in each group, the first two recipients will be treated as sentinel recipients (at least one will receive the IMP). If no reactogenicity and adverse events that are considered to be related to IMP (possibly, probably or definitely related) and are graded as severe or worse (Grade 3 or 4 on the DAIDS Toxicity Table) occur within 7 days after injection, the second volunteer may be injected. The same process will be followed after the second injection. If no events meeting the criteria described above occur within 7 days after the second volunteer is injected, then the

above do occur for the first two volunteers, they will be reviewed by the Safety Review Board (SRB) to determine whether further injections may proceed.

Dose escalation

Once all volunteers in the first dosage group (Group A) have received their injection, enrolment into the next higher dosage group / assignment of new allocation numbers will pause. Safety data through the Day 42 post-injection visit for all volunteers in the dosage group will be reviewed by the SRB prior to allowing volunteers into the second dosage group (Group B). Specific safety criteria to allow dose escalation are detailed in Section 17.2.2. If criteria for dose escalation are met, Group B enrolment will proceed. Once safety data through Day 42 post-injection visit is available for all volunteers in Group B, all available safety data (Groups A and B) will be reviewed by the SRB prior to allowing volunteers into Group C. If criteria for dose escalation are met, Group C enrolment will proceed. Once safety data through Day 56 post-injection visit is available for all volunteers in Group C, all available safety data (Groups A, B and C) will be reviewed by the SRB. In addition, PG9 antibody expression will be evaluated.

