- If safety criteria to allow dose escalation are met and PG9 antibody expression is sufficient (~150ug/ml), the study will proceed to enrol an expanded number of volunteers at the Group C dose (Group C1) and enrolment into Group D will not occur.
- Otherwise, if PG9 antibody expression is not sufficient but safety criteria for dose escalation are met, the study will proceed to enrol the highest dose level (Group D). Safety and tolerability will be evaluated by the SRB over at least 56 days for volunteers in Group D. Once safety data through Day 56 post-injection visit is available for all volunteers in Group D, all available safety data (Groups A, B, C and D) will be reviewed by the SRB. If criteria for dose escalation are met, the study will proceed to enrol an expanded number of volunteers at the Group D dose (Group D1).

In the study all groups will be randomized in a 3:1 ratio of active product to placebo with the exception of Group D1, where 5 volunteers will be randomized in a 4:1 ratio of active product to placebo.

Table 5.0-1 Study Design

	Number Active/						
Group	Placebo	Dose (vg)	Route	Month 0			
А	3/1	4x10 ¹² or Placebo	IM	х			
SRB revie	SRB review						
в	3/1	4x10 ¹³ or Placebo	IM	х			
SRB review							
с	3/1	8x10 ¹³ or Placebo	ІМ	x			
SRB review to determine progression to either C1, or D and D1							
C1	9/3	8x10 ¹³ or Placebo	IM	х			
Total Number of Volunteers: 24 (18/6)							
OR							
D	3/1	1.2x10 ¹⁴ or Placebo	IM	Х			
SRB review							
D1	4/1	1.2x10 ¹⁴ or Placebo	IM	Х			
Total Number of Volunteers: 21 (16/5)							

IM=Intramuscular

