9.1.5 Other Adverse Events

Other adverse events (AEs) will be collected through Day 168. Serious Adverse Events (SAEs) will be collected throughout the entire study period. Open ended

questions will be asked at time points according to the Schedule of Procedures (Appendix A). All adverse events will be graded using Appendix B, Adverse Event Severity Assessment Table, as a guideline and will be assessed for causality to the IMP. For more information regarding adverse events refer to Section 10.0, Adverse Events.

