10.2 Assessment of Severity of Adverse Events

The following general criteria should be used in assessing adverse events as mild, moderate, severe or very severe at the time of evaluation:

Grade 1 (Mild): Symptoms causing no or minimal interference with usual social and functional activities

Grade 2 (Moderate): Symptoms causing greater than minimal interference with usual social and functional activities

Grade 3 (Severe): Symptoms causing inability to perform usual social and functional activities

Grade 4 (Very Severe): Symptoms causing inability to perform basic self-care functions OR Medical or operative intervention indicated to prevent permanent impairment, persistent disability, or death

Guidelines for assessing the severity of specific adverse events and laboratory abnormalities are listed in Appendix B, Adverse Event Severity Assessment Table.

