17.2.1 Timing and content of Interim Safety Reviews

Interim safety reviews will be conducted by the SRB at the following times:

- Once all volunteers in Group A have been followed for at least 42 days after injection
- Once all volunteers in Group B have been followed for at least 42 days after injection
- Once all volunteers in Group C have been followed for at least 56 days after injection
- Once all volunteers in Group D have been followed for at least 56 days after injection

The SRB will be asked to review the following unblinded data at the planned interim reviews. Data will include all accumulated safety data available at the time:

- Summary of reactogenicity (i.e., solicited adverse events)
- All clinical adverse events judged by the Principal Investigator or designee to be possibly, probably or definitely related to the IMP and all pIMD
- All laboratory adverse events confirmed on retest and judged by the Principal Investigator or designee to be possibly, probably, or definitely related to IMP and/or clinically significant
- Summary of ECG findings. The SRB will be provided copies of specific ECGs if they request.
- Summary of cardiac troponin I results. The SRB will be provided individual cardiac troponin I results if they request.
- All SAEs
- PG9 antibody level (for Group C review only, to determine if higher dose is indicated or if enrolment should be expanded to C1)

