17.4 Criteria for Pausing the Study

Enrolments and injections will be paused, a formal study halt will be submitted to the MHRA as a substantial amendment, and a safety review conducted by the SRB for any of the following criteria:

- 1. One volunteer develops a Grade 3 or 4 adverse event that is judged to be possibly, probably or definitely related to IMP;
- 2. Grade 2 adverse events that persists for more than 7 days that is possibly, probably or definitely related to the IMP;
- 3. One volunteer experiences a serious adverse event that is probably or definitely related to the IMP, or two or more subjects experience similar serious adverse events which are possibly related to the IMP;
- 4. There is a volunteer death assessed as possibly, probably or definitely related to the IMP;
- 5. One volunteer shows evidence of disease that might be due to immune complexes and is judged to be possibly, probably or definitely related to IMP, such as acute arthritis, severe generalized rash, or glomerulonephritis;
- 6. A 5-fold increase in ALT within 10 weeks after IMP administration which is not responsive to oral corticosteroids and is judged to be possibly, probably or definitely related to IMP.

The Sponsor will request a review by the SRB, (or the SRB chair if other SRB members cannot be convened), to be held within 2 business days of the Sponsor learning of the

event. The individual volunteer(s)/or study may be unblinded at the discretion of the SRB.

Following this review, the SRB will make a recommendation regarding the continuation or suspension of the vaccinations or the trial and communicate this decision immediately to the Sponsor. If the SRB decision is to restart enrolments and injections, then a further substantial amendment will be submitted to the MHRA including all appropriate safety data and justification to restart. The Sponsor then will inform the Principal Investigator of the MHRA decision.

Additional *ad hoc* review may be specifically requested by the Sponsor, the Principal Investigator(s) or by the SRB.

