Comment: Some laboratori same tests; values should b Bilirubin (Total)	e graded according to the i	ranges for Bicarbonate as lis	sted above.	
Adult and Pediatric > 14 days	1.1 – 1.5 x ULN	1.6 – 2.5 x ULN	2.6 – 5.0 x ULN	> 5.0 x ULN
Infant* [†] , ≤ 14 days (non-hemolytic)	NA	20.0 – 25.0 mg/dL 342 – 428 µmol/L	25.1 – 30.0 mg/dL 429 – 513 μmol/L	> 30.0 mg/dL > 513.0 µmol/L
Infant* [†] , ≤ 14 days (hemolytic)	NA	NA	20.0 – 25.0 mg/dL 342 – 428 μmol/L	> 25.0 mg/dL > 428 µmol/L
Calcium, serum, high				
Adult and Pediatric ≥ 7 days	10.6 – 11.5 mg/dL 2.65 – 2.88 mmol/L	11.6 – 12.5 mg/dL 2.89 – 3.13 mmol/L	12.6 – 13.5 mg/dL 3.14 – 3.38 mmol/L	> 13.5 mg/dL > 3.38 mmol/L
Infant* [⁺] , < 7 days	11.5 – 12.4 mg/dL 2.88 – 3.10 mmol/L	12.5 – 12.9 mg/dL 3.11 – 3.23 mmol/L	13.0 – 13.5 mg/dL 3.245 – 3.38 mmol/L	> 13.5 mg/dL > 3.38 mmol/L
Calcium, serum, low			6.1 – 6.9 mg/dL	< 6.1 mg/dL
Calcium, serum, low Adult and Pediatric ≥ 7 days	7.8 – 8.4 mg/dL 1.95 – 2.10 mmol/L	7.0 – 7.7 mg/dL 1.75 – 1.94 mmol/L	1.53 – 1.74 mmol/L	< 1.53 mmol/L

LABORATORY				
PARAMETER	GRADE 1 MILD	GRADE 2 MODERATE	GRADE 3 SEVERE	GRADE 4 VERY SEVERE
Cardiac troponin I (cTnI)	NA	NA	NA	Levels consistent with myocardial infarction or unstable angina as defined by the manufacturer
Cardiac troponin T (cTnT)	NA	NA	NA	≥ 0.20 ng/mL OR Levels consistent with myocardial infarction or unstable angina as defined by the manufacturer
Cholesterol (fasting)				
Adult ≥ 18 years	200 – 239 mg/dL 5.18 – 6.19 mmol/L	240 – 300 mg/dL 6.20 – 7.77 mmol/L	> 300 mg/dL > 7.77 mmol/L	NA
Pediatric < 18 years	170 – 199 mg/dL 4.40 – 5.15 mmol/L	200 – 300 mg/dL 5.16 – 7.77 mmol/L	> 300 mg/dL > 7.77 mmol/L	NA
Creatine Kinase	$3.0 - 5.9 \text{ x ULN}^{\dagger}$	$6.0 - 9.9 \times ULN^{\dagger}$	$10.0 - 19.9 \times ULN^{\dagger}$	\geq 20.0 x ULN [†]
Creatinine	1.1 – 1.3 x ULN [†]	1.4 – 1.8 x ULN [†]	1.9 – 3.4 x ULN [†]	\geq 3.5 x ULN [†]

LABORATORY				
PARAMETER	GRADE 1	GRADE 2	GRADE 3	GRADE 4
	MILD	MODERATE	SEVERE	VERY SEVERE
Glucose, serum, high				
Nonfasting	116 – 160 mg/dL	161 – 250 mg/dL	251 – 500 mg/dL	> 500 mg/dL
	6.44 – 8.88 mmol/L	8.89 – 13.88 mmol/L	13.89 – 27.75 mmol/L	> 27.75 mmol/L
Fasting	110 – 125 mg/dL	126 – 250 mg/dL	251 – 500 mg/dL	> 500 mg/dL
	6.11 – 6.94 mmol/L	6.95 – 13.88 mmol/L	13.89 – 27.75 mmol/L	> 27.75 mmol/L
Glucose, serum, low				
Adult and Pediatric	55 – 64 mg/dL	40 – 54 mg/dL	30 – 39 mg/dL	< 30 mg/dL
≥ 1 month	3.05 – 3.55 mmol/L	2.22 – 3.06 mmol/L	1.67 – 2.23 mmol/L	< 1.67 mmol/L

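### Section 17.4 has no troponin trigger: a related, clinically significant troponin I rise below the infarction/unstable-angina level stops the next group from opening but does not by itself pause injections.

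*Protocol*

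**What the plan says.** Section 17.2.2 lists what must hold before the next dose level opens. One criterion is "No confirmed and clinically significant elevated cardiac troponin I levels", with no condition on grade or relatedness. A parallel criterion covers new ECG findings that suggest cardiac disease. Section 5.0 also requires the escalation criteria to be met before the expansion groups C1 or D1 open.

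Section 17.4 has six pause criteria. The first is "One volunteer develops a Grade 3 or 4 adverse event that is judged to be possibly, probably or definitely related to IMP". The others are:

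- item 2: a related Grade 2 event lasting more than 7 days;
- item 3: related SAEs;
- item 4: a related death;
- item 5: related disease that might be due to immune complexes;
- item 6: a steroid-unresponsive, related ALT rise.

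Grades come from Appendix B: "All adverse events will be graded using Appendix B, Adverse Event Severity Assessment Table, as a guideline" (9.1.5). Its troponin I row is NA for Grades 1 to 3, and Grade 4 reads "Levels consistent with myocardial infarction or unstable angina as defined by the manufacturer". The general scale in 10.2 starts at Grade 1 with "Symptoms causing no or minimal interference with usual social and functional activities".

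The last planned Safety Review Board (SRB) review in 17.2.1 is "Once all volunteers in Group D have been followed for at least 56 days after injection", or Group C at Day 56 if the study expands to C1. On sentinel dosing, 5.0 says "In Groups A-D, the first 3 volunteer injections will be separated by 7 days".

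**The concern.** Cardiac inflammation is the preclinical finding for which the protocol says a product effect cannot be excluded: 3 of 40 mice at the top dose, none among controls (2.4). Troponin and ECG were chosen to watch for it. Yet a result serious enough to keep the next group closed need not stop injections in the group being dosed.

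For Groups A to D, a planned SRB review follows, so such a result would be weighed before anyone enters the next group. For C1 and D1 no planned review follows. Whether dosing continued after a related, silent troponin rise would rest on the discretion of the investigator, the sponsor or the SRB. The product is a single-dose vector built for long expression, so an injection cannot be withdrawn once given.

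**Working it through.** There is no planned figure to reproduce. The check compares the rules and then counts exposure.

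**1. Do the 17.2.2 criteria have a counterpart in 17.4?**

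| 17.2.2 bars progression for | Counterpart in 17.4 |
|---|---|
| SAE probably or definitely related | item 3 |
| Related death | item 4 |
| Related disease that might be immune mediated | item 5 (narrower: immune complexes) |
| New ECG finding suggesting cardiac disease | none named; largely reached through items 1 and 2 |
| Confirmed, clinically significant troponin I rise | none named |

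**2. Can a troponin rise reach items 1 or 2 by its grade?** Three of the four troponin I grades are NA, so below the infarction/unstable-angina level the table assigns none. Appendix B is a guideline, and the general scale in 10.2 turns mainly on symptoms and function, so a silent rise would normally sit at Grade 1. Neither item is met by the laboratory result alone. ALT, by contrast, has a full scale (Grade 3 from 5.1 x ULN) and its own item 6.

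**3. Can ECG findings reach items 1 or 2?** Mostly yes, if related. Grade 3 includes testing consistent with ischaemia, QTc of at least 0.50 s or an increase of at least 0.06 s, and Type II second-degree AV block. A QTc increase of 0.03 to 0.05 s is Grade 2 and pauses the study if it lasts more than 7 days.

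**4. Who is dosed after the last planned SRB review?**

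- D1: 5 of 21 volunteers; active share 4/(3+3+3+3+4) = 4/16 = 25%.
- C1: 12 of 24 volunteers; active share 9/(3+3+3+9) = 9/18 = 50%.

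**5. How many injections could a trigger avoid at most?** Suppose the first volunteer in the group is active and shows the rise.

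- D1: 5 - 1 = 4 further injections, 4 - 1 = 3 of them active.
- C1: 12 - 1 = 11 further injections, 9 - 1 = 8 of them active.

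These are ceilings. Section 9.1.10 leaves troponin out at Day 3, so the first post-dose value is at Day 7 ± 3, that is Day 4 to Day 10, and confirmation on retest comes later still. Anyone dosed before then is not protected by any troponin rule.

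**6. How likely is it that the rule would matter?** The protocol gives no rate. For an assumed true rate p of such a rise per active recipient, the chance of at least one case is 1 - (1 - p)^n:

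| p (assumed) | D1, n = 4 | C1, n = 9 |
|---|---|---|
| 5% | 18.5% | 37% |
| 10% | 34% | 61% |
| 20% | 59% | 87% |
| 30% | 76% | 96% |

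**7. Are the data available?** Yes. Appendix A schedules troponin I on Days 7, 14, 21, 28, 35, 42, 49, 56, 70, 84, 112, 140, 168, 252 and 336: 15 post-dose tests per volunteer.

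**The case against.** The strongest reply is that the two sections do different jobs. 17.2.2 decides whether to proceed. 17.4 triggers a formal regulatory halt with a substantial amendment, and a second one to restart. A broader rule for progression than for a halt is an ordinary choice. That stands: this is not a contradiction, and a reader who infers one goes further than the text.

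A reader might also infer that injections would carry on regardless. The documents do not support that. A troponin rise can reach a pause by several routes:

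- reading it as testing consistent with ischaemia (Grade 3);
- the 10.2 Grade 4 clause on intervention to prevent permanent impairment;
- item 3, if it qualifies as an SAE and is probably or definitely related, or if two similar possibly related SAEs occur;
- item 5, whose examples are open-ended, although it speaks of immune complexes and does not plainly cover all cardiac inflammation.

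The Protocol Safety Review Team reviews data weekly until 6 weeks after the last injection, and ad hoc SRB review can be requested. All these routes depend on judgement; none is compelled by the troponin result.

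Two further inferences fail. The ECG criterion is not left open in the same way (step 3). Nor is it certain that C1 and D1 lack spacing: 5.0 names only Groups A to D, but 2.7 can be read as spacing the first three injections in every dose group. Spacing of 7 days would still not be a troponin trigger, and the sentinel stop itself needs a related Grade 3 or 4 event.

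Finally, the width of the gap cannot be shown. The only troponin I figure in the protocol is the entry limit of 0.04 ng/mL. Neither a clinically significant rise nor the manufacturer's level has a number. If that level lies close to 0.04 ng/mL, the gap is small.

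**Conclusion.** The point holds in limited form. A related, confirmed, clinically significant but silent troponin I rise below the infarction/unstable-angina level forces no pause under 17.4, although the same result blocks progression under 17.2.2. The consequence is greatest in D1 (25% of active recipients) or C1 (50%), where no planned SRB review follows.

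The 4 or 11 further injections are upper bounds and should not be read as injections that a trigger would have saved; the number could be zero. The conclusion assumes that the rise lies below the Grade 4 level, causes no graded symptoms, and is not brought under another item by judgement. The document cannot say how often that would occur.

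This is worth considering rather than essential. The last summary of changes says enrolment was complete, so the practical effect on this trial is limited. The wording would matter most if it were reused for a later study of the same product.

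**What to change.** Add one item to 17.4, stated to apply to all groups including C1 and D1: *One volunteer has a cardiac troponin I elevation that is confirmed on retest, clinically significant, and judged at least possibly related to IMP.*

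The relatedness condition is absent from the 17.2.2 troponin criterion but matches the other items in 17.4 and limits false alarms. A matching clause for cardiologist-confirmed ECG findings is optional, since most are already covered.

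No new tests are needed: troponin is already scheduled, and confirmation on retest is already used for the SRB data in 17.2.1. The cost is an occasional extra halt and restart amendment for a finding that proves benign. Some judgement remains, because clinical significance and relatedness are still the investigator's call, but once both are affirmed the pause would no longer be optional.

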17.3 Medical Advisory Panel

In addition to the SRB, a Medical Advisory Panel with physicians with expertise in the use of immunosuppressive drugs and the management of immune-mediated disease such as immune nephritis and hepatitis will be formed at the clinical site institution. The Medical Advisory Panel will be knowledgeable about the protocol and available to provide rapid evaluation and management of potential immune mediated diseases, if they occur in study volunteers.

17.4 Criteria for Pausing the Study

Enrolments and injections will be paused, a formal study halt will be submitted to the MHRA as a substantial amendment, and a safety review conducted by the SRB for any of the following criteria:

- 1. One volunteer develops a Grade 3 or 4 adverse event that is judged to be possibly, probably or definitely related to IMP;
- 2. Grade 2 adverse events that persists for more than 7 days that is possibly, probably or definitely related to the IMP;
- 3. One volunteer experiences a serious adverse event that is probably or definitely related to the IMP, or two or more subjects experience similar serious adverse events which are possibly related to the IMP;
- 4. There is a volunteer death assessed as possibly, probably or definitely related to the IMP;
- 5. One volunteer shows evidence of disease that might be due to immune complexes and is judged to be possibly, probably or definitely related to IMP, such as acute arthritis, severe generalized rash, or glomerulonephritis;
- 6. A 5-fold increase in ALT within 10 weeks after IMP administration which is not responsive to oral corticosteroids and is judged to be possibly, probably or definitely related to IMP.

The Sponsor will request a review by the SRB, (or the SRB chair if other SRB members cannot be convened), to be held within 2 business days of the Sponsor learning of the

event. The individual volunteer(s)/or study may be unblinded at the discretion of the SRB.

Following this review, the SRB will make a recommendation regarding the continuation or suspension of the vaccinations or the trial and communicate this decision immediately to the Sponsor. If the SRB decision is to restart enrolments and injections, then a further substantial amendment will be submitted to the MHRA including all appropriate safety data and justification to restart. The Sponsor then will inform the Principal Investigator of the MHRA decision.

Additional *ad hoc* review may be specifically requested by the Sponsor, the Principal Investigator(s) or by the SRB.

17.5 Study Supervision

The SRB, the IAVI Chief Medical Officer (CMO) and the IAVI Medical Monitor(s) have access to progress report(s) of this study. Close cooperation will be necessary to track study progress, respond to queries about proper study implementation and management, address issues in a timely manner, and assure consistent documentation, and share information effectively. Rates of accrual, retention, and other parameters relevant to the site's performance will be regularly and closely monitored by the study team.

